3.3 EVERY TOXICITY

In the following table, the number and relative frequencies of patients with at least one toxicity are summarised:

Table 116 Patients with at least one toxicity during follow-up

	Cohort 1	Cohort 2	Cohort 3	Cohort 4	Total
At least one toxicity	n (% , CI 95%)				
Yes					
No					
Total	n (100%)				

In the following table, every toxicity grade ≥ 3 will be summarised, separately in each one of the 4 cohorts and in overall.

Table 117 Every toxicity grade ≥ 3 in overall and by cohort

	Cohort 1	Cohort 2	Cohort 3	Cohort 4	Total
Toxicities	n (% , CI 95%)				
Toxicity 1 G1					
Toxicity 1 G2					
Toxicity 1 G3					
Toxicity 1 G4					
Toxicity 2 G1					
Toxicity 2 G2					
Toxicity 2 G3					
Toxicity 2 G4					
Toxicity 3 G1					

Toxicity 3 G2

Toxicity 3 G3

Toxicity 3 G4

...

4 EXPLORATORY ANALYSES

The aims of this section are:

- To evaluate biochemical response (changes in CgA and NSE levels) and its association with response rate and progression-free survival.
- To assess whether baseline tumor and blood biomarkers may be predictive of response to durvalumab and tremelimumab therapy.
- To explore additional hypotheses related to biomarkers and relationship to durvalumab and tremelimumab efficacy and/or toxicity and neuroendocrine tumors evolution that may arise from internal or external research activities.

4.1 LOGISTIC REGRESSION: PREDICTOR FACTORS OF RESPONSE (CBR AT 9 MONTHS) IN EACH COHORT

A multivariate analysis will be carried out using the Logistic Regression model in order to determine predictor factors for response (CBR at 9 months) **in each cohort**. Firstly univariate analysis are carried out separately for each one of the possible predictor factors to decide which variables are entered in the multivariate models; only those with a statistical association with the dependent variable would be selected. Backward elimination stepwise process would be used to select the model. In the first step all possible predictors are entered in the model and in each step, the variable that is least significant (that is, the one with the largest P value) is removed and the model is refitted. Each subsequent step removed the least significant variable in the model until all remaining variables have individual P values smaller than 0.05.

Table 118 Univariate Logistic Regression for Response (CBR at 9 months) in cohort 1 (Full Analysis Set)

p-value (variable)	OR	CI 95% of OR	N	p-value (categories)
Factor 1	Category 1			
	Category 2			

Factor 2	Category 1
	Category 2
Factor 3	Category 1
	Category 2
Factor 4	Category 1
	Category 2
...	Category 1
	Category 2

Table 119 Final multivariate Logistic Regression for Response (CBR at 9 months) in cohort 1 (Full Analysis Set)

	p-value (variable)	OR	CI 95% of OR	N	p-value (categories)
Factor 1	Category 1				
	Category 2				
Factor 2	Category 1				
	Category 2				
...	Category 1				
	Category 2				

Table 120 Univariate Logistic Regression for Response (CBR at 9 months) in cohort 2 (Full Analysis Set)

	p-value (variable)	OR	CI 95% of OR	N	p-value (categories)
Factor 1	Category 1				
	Category 2				

Factor 2	Category 1
	Category 2
Factor 3	Category 1
	Category 2
Factor 4	Category 1
	Category 2
...	Category 1
	Category 2

Table 121 Final multivariate Logistic Regression for Response (CBR at 9 months) in cohort 2 (Full Analysis Set)

	p-value (variable)	OR	CI 95% of OR	N	p-value (categories)
Factor 1	Category 1				
	Category 2				
Factor 2	Category 1				
	Category 2				
...	Category 1				
	Category 2				

Table 122 Univariate Logistic Regression for Response (CBR at 9 months) in cohort 3 (Full Analysis Set)

	p-value (variable)	OR	CI 95% of OR	N	p-value (categories)
Factor 1	Category 1				
	Category 2				
Factor 2	Category 1				

	Category 2
Factor 3	Category 1
	Category 2
Factor 4	Category 1
	Category 2
...	Category 1
	Category 2

Table 123 Final multivariate Logistic Regression for Response (CBR at 9 months) in cohort 3 (Full Analysis Set)

	p-value (variable)	OR	CI 95% of OR	N	p-value (categories)
Factor 1	Category 1				
	Category 2				
Factor 2	Category 1				
	Category 2				
...	Category 1				
	Category 2				

Table 124 Univariate Logistic Regression for Response (CBR at 9 months) in cohort 4 (Full Analysis Set)

	p-value (variable)	OR	CI 95% of OR	N	p-value (categories)
Factor 1	Category 1				
	Category 2				
Factor 2	Category 1				
	Category 2				

Factor 3	Category 1
	Category 2
Factor 4	Category 1
	Category 2
...	Category 1
	Category 2

Table 125 Final multivariate Logistic Regression for Response (CBR at 9 months) in cohort 4 (Full Analysis Set)

	p-value (variable)	OR	CI 95% of OR	N	p-value (categories)
Factor 1	Category 1				
	Category 2				
Factor 2	Category 1				
	Category 2				
...	Category 1				
	Category 2				

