11.2. Methods of statistical analyses

Strategic decisions about future development of immune therapy in neuroendocrine tumors will be available after the results of this trial.

Summary tables (descriptive statistics and frequency tables) will be provided for all baseline variables, efficacy variables, and safety variables, as appropriate. Continuous variables will be summarized with descriptive statistics (mean, standard deviation, range, and median). Ninety-five (95) percent confidence intervals (95% CI) may also be presented, as appropriate. Frequency counts and percentage of subjects within each category will be provided for categorical data.

The primary efficacy analysis will be performed using the binomial test procedure. Missing data will be treated using statistical multiple random imputation.

Secondary endpoints will be summarized with descriptive statistics. Continuous variables will be summarized with n, mean, standard deviation, and range, frequency counts and percentage of subjects within each category will be provided for categorical data. Multivariate regression models will be used to study relations between explanatory variables and primary endpoint. Survival analysis will be performed to analyze PFS, Kaplan-Meier curves will be presented and possible comparisons will be tested using the log-rank test or the Cox proportional hazard model for multivariate analysis, hazard ratios (HR) and their 95% confidence interval (CI95%) will be provided. Patients with lost of follow-up or treatment discontinuation will be included in the final analysis of primary endpoint if they have at least one tumor evaluation and considered as censored data for survival endpoints.

R software version 3.2.1 will be used for all analysis.

Safety Analyses

Safety analyses will be based on the Safety Analysis Set. All safety analyses will be summarized separately by cohort. Adverse events and serious adverse events, laboratory test results, physical examination findings and vital signs, and their changes from baseline will be summarized using descriptive statistics. Abnormal values will be flagged.

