3.6 SAMPLE SIZE

Sample size has been calculated using one-sample Superiority test (function OneSampleProportion. (NIS) of the Trial Size package of R software). According to previous knowledge, it is estimated that the reference value for the likelihood to be progression-free at 9 months is 30% and we expect an increase of 20% with a superiority margin of 10%. With a unilateral alpha level of 5% and 80% power, we estimate to include 28 patients per group, with an expected lost to follow-up rate of 10%, a final sample size in each 1, 2 and 3 cohort will include 31 patients.

For cohort 4, and according to previous knowledge, it is estimated that the reference proportion of patients being alive at 9 months is 13% and we expect an increase of 10% with a superiority margin of 5%. With a unilateral alpha level of 5% and 80% power, we estimate to include 30 patients per group, with an expected lost to follow-up rate of 10%, a final sample size will include 33 patients.

Summarizing, total sample size will include 126 patients: 31 patients for cohorts 1 to 3, and 33 for cohort 4.

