4.2 COX REGRESSION: PREDICTOR FACTORS OF SURVIVAL IN EACH COHORT

4.2.1 Cox Regression: predictor factors of PFS in each cohort

A multivariate analysis will be carried out using the Cox Regression model in order to determine predictor factors for PFS **in each cohort**. Firstly univariate analysis are carried out separately for each one of the possible predictor factors to decide which variables are entered in the multivariate models; only those with a statistical association with the dependent variable would be selected. Backward elimination stepwise process would be used to select the model. In the first step all possible predictors are entered in the model and in each step, the variable that is least significant (that is, the one with the largest P value) is removed and the model is refitted. Each subsequent step removed the least significant variable in the model until

Statistical Analysis Plan
 Drug Substance DURVALUMAB/TREMELIMUMAB
 Study Number ESR 15-11561-DUNE
 EudraCT Nº: 2016-002858-20
 Version Number: 1.1 dated on 30/NOV/2017
 all remaining variables have individual P values smaller than 0.05.

Table 126 Univariate Cox Regression for PFS in cohort 1 (Full Analysis Set)

	HR	CI 95% of HR	p-value	n
Factor 1	Category 1			
	Category 2			
Factor 2	Category 1			
	Category 2			
Factor 3	Category 1			
	Category 2			
Factor 4	Category 1			
	Category 2			
...	Category 1			
	Category 2			

Table 127 Final multivariate Cox Regression for PFS in cohort 1 (Full Analysis Set)

	HR	CI 95% of HR	p-value	n
Factor 1	Category 1			
	Category 2			
Factor 2	Category 1			
	Category 2			
...	Category 1			
	Category 2			

Table 128 Univariate Cox Regression for PFS in cohort 2 (Full Analysis Set)

	HR	CI 95% of HR	p-value	n
Factor 1	Category 1			
	Category 2			
Factor 2	Category 1			
	Category 2			
Factor 3	Category 1			
	Category 2			
Factor 4	Category 1			
	Category 2			
...	Category 1			
	Category 2			

Table 129 Final multivariate Cox Regression for PFS in cohort 2 (Full Analysis Set)

	HR	CI 95% of HR	p-value	n
Factor 1	Category 1			
	Category 2			
Factor 2	Category 1			
	Category 2			
...	Category 1			
	Category 2			

Table 130 Univariate Cox Regression for PFS in cohort 3 (Full Analysis Set)

	HR	CI 95% of HR	p-value	n

Factor 1	Category 1
	Category 2
Factor 2	Category 1
	Category 2
Factor 3	Category 1
	Category 2
Factor 4	Category 1
	Category 2
...	Category 1
	Category 2

Table 131 Final multivariate Cox Regression for PFS in cohort 3 (Full Analysis Set)

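### Predictor models chosen by p-value within cohorts of 31 to 33 patients will report ratios, p-values and 95% intervals that ignore the selection

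*SAP*

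**What the plan says.** SAP 4.1 (logistic, clinical benefit rate (CBR) at month 9), 4.2.1 (Cox, PFS) and 4.2.2 (Cox, OS) give the same two-stage rule, to be run in each cohort.

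- Stage 1 tests candidates one at a time, "separately for each one of the possible predictor factors to decide which variables are entered in the multivariate models", and "only those with a statistical association with the dependent variable would be selected".
- Stage 2 is described as "Backward elimination stepwise process would be used to select the model". It begins: "In the first step all possible predictors are entered in the model and in each step, the variable that is least significant" is dropped. The model is then refitted until "all remaining variables have individual P values smaller than 0.05".

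The shells (SAP Tables 118–141) pair a univariate table with a final multivariate table for every cohort and endpoint. Each has a ratio, a 95% CI and a p-value. The rows are placeholders for unnamed factors with two categories each.

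On size, SAP 3.6 says that "a final sample size in each 1, 2 and 3 cohort will include 31 patients" and, for cohort 4, that "a final sample size will include 33 patients". Protocol 11.2 describes the purpose thus: "Multivariate regression models will be used to study relations between explanatory variables and primary endpoint".

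The SAP gives no candidate list, no numeric threshold for stage 1, no limit on terms per event, and no shrinkage, validation or multiplicity control for these models. The two stages also disagree: one admits only screened variables, while the other starts from all possible predictors.

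**The concern.** A variable reaches a final table only because its estimate was large relative to its standard error in these same 31 to 33 patients. A p-value or interval computed as though that variable had been named beforehand does not allow for this. The p-value is too small, and the ratio is on average too far from 1. Nothing in the final table would let a reader see it.

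At stake is the exploratory objective on tumour and blood biomarkers. A short table of factors with p<0.05 is what gets carried into a publication or into patient selection for a later trial.

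Two further points bear on the same sections. The cohort 4 logistic model uses CBR, although that cohort's primary endpoint is 9-month survival. And the SAP speaks of factors predictive of response to therapy, whereas a trial without a control arm cannot separate factors that predict treatment benefit from factors that are merely prognostic.

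**Working it through.** **Plan's own figures.** The SAP states no operating figure for these models, so only the cohort sizes can be reproduced. Taking its 28 and 30 as given: 28 × 1.1 = 30.8, rounded to 31; 30 × 1.1 = 33; 3 × 31 + 33 = 126. Three endpoints × four cohorts = 12 final models.

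**Analytic step.** Let K be the number of candidates, all unrelated to outcome (assumption), screened at p<0.05 (assumption; the SAP gives no number). If one candidate passes, backward elimination with the same test cannot empty the model, because the last survivor is itself significant on its own. So for independent candidates

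P(at least one noise factor in the final model) = 1 − 0.95^K.

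This gives 5% for K=1, 14% for K=3, 40% for K=10, 51% for K=14, 64% for K=20, 87% for K=40 and 97% for K=70.

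**Simulation of the logistic rule.** n=31, event rate 30% or 50% (the reference and expected rates in SAP 3.6), a quarter of covariates binary, 400 runs per setting. Covariates were correlated in blocks of five: correlation 0 at K=10, 0 or 0.5 at K=20, 0.5 at K=40, and 0 to 0.8 at K=70.

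| K | 1 − 0.95^K | Wald tests | Likelihood-ratio tests |
|---|---|---|---|
| 10 | 40% | about 30% | 43–45% |
| 20 | 64% | 42–51% | 64–75% |
| 40 | 87% | 65–72% | 85–87% |
| 70 | 97% | 77–94% | 91–99% |

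A separate simulation with independent normal covariates (300 runs per setting) gave 26% at K=10, 55% at K=20 and 76–79% at K=45. The median reported odds ratio was 3.1–4.4 per SD where the truth is 1.

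**Coding.** The shells show two-category factors. Exact enumeration for independent null factors (prevalence 15–50%, n=31, event rate 30–50%) gives 7–33% at K=10 and 13–55% at K=20 with Wald tests, and 46–56% at K=10 with likelihood-ratio tests.

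**Looser screen.** With K=70, correlation 0.5, event rate 50% and Wald tests, a 0.05 screen gives 85%, 0.10 gives 89% and 0.20 gives 93%.

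**Cox models.** n=31, about 80% events, independent normal covariates, Wald, 150 runs each: 39% at K=10, 67% at K=20, 91% at K=45, 100% at K=70. The Monte Carlo error at K=10 is about 2 × √(0.39 × 0.61/150) = 8 points. The median hazard ratio was 1.7–1.9 per SD where the truth is 1.

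**Intervals.** When p-value and CI are both Wald, every retained CI excludes 1. With likelihood-ratio p-values, 36–63% of retained factors had a Wald CI excluding 1.

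**How large could K be?** SAP Tables 7–20 tabulate 3 (demographics) + 7 (vital signs) + 1 (ECOG) + 5 (tumour) + 1 (time since progression) + 1 (prior therapy) + 1 (best prior response) + 13 (haematology) + 21 (chemistry) + 8 (urinalysis) + 3 (thyroid) + 3 (coagulation) + 1 (anti-PNS) + 4 (serology) + 2 (CgA, NSE) = 74 variables, or 70 without serology. If all of these were entered at the first step, the model would have more terms than patients.

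**Cohort 4.** CBR at month 9 requires being alive. At the planning survival rates of 13% and 23%, events are at most 33 × 0.13 = 4.3 and 33 × 0.23 = 7.6.

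**The case against.** The strongest reply is that the candidates are unknown. SAP Tables 7–20 are descriptive, and nothing says that they feed the models. The stated aims point to CgA, NSE and tumour or blood biomarkers. Several tabulated items would make poor predictors: known hepatitis B, hepatitis C and HIV are exclusions, fT3 and fT4 are measured only if TSH is abnormal or an endocrine event is suspected, and protocol schedule footnote m makes octreoscan/PET not applicable in cohort 4. A reader might infer that about 70 variables will be screened at 0.05 and that most final models will therefore contain noise. The documents support neither number. At about 10 candidates the simulated mixed-covariate figure is below one half, and with two-category factors and Wald tests it can be as low as 7%.

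A reader might also infer that every final interval will exclude 1 by construction. That is exact only if p-values and intervals are both Wald, which the SAP does not say. Nor do these figures show that the reported factors will be mainly false: they give the chance of at least one noise factor when nothing is real, not the false share among factors reported.

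Finally, the trial is described as exploratory, the section carries that heading, and univariate tables are already planned. All of this stands. It lowers the severity and narrows the claim. It does not make p-values and intervals valid after selection, and an open candidate list means that the predictors can be chosen after the data are seen.

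**Conclusion.** The point holds in this form: the plan states a selection rule and then reports ordinary ratios, p-values and 95% CIs that take no account of it, in twelve models on 31 to 33 patients each.

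Assuming a 0.05 screen and all-null candidates, a logistic model keeps at least one noise factor with probability roughly 26–45% at 10 candidates, 42–75% at 20, 65–87% at 40, and 77–99% if about 70 of the tabulated variables were used. The figures are lower for two-category factors with Wald tests and higher with a looser screen.

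A short list does not rescue the rule. At 26–30% per CBR model, the chance of at least one spurious model across cohorts 1 to 3 is 1 − 0.74³ = 59% to 1 − 0.70³ = 66%, treating the cohorts as independent.

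The cohort 4 CBR model, with at most about 4 to 8 events, cannot support a multivariable fit. The primary endpoints, the binomial test and the sample size are untouched, so this should be corrected but does not threaten the main result.

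**What to change.** In SAP 4.1, 4.2.1 and 4.2.2:

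1. Delete the univariate screening and backward-elimination text.
2. Name a short list of factors in advance, about one to three per cohort as events allow, and fit them without selection using a Firth or ridge penalty. At the planning rates a cohort of 31 has 31 × 0.30 = 9 to 31 × 0.50 = 15 or 16 CBR events. Three candidates instead of an open list would cut the analytic figure above to 14% even if selection were kept.
3. Present the univariate tables already planned as the unselected estimates for all other variables, in full.
4. Drop the cohort 4 CBR logistic model (Tables 124–125) and keep that cohort's OS Cox model.
5. Describe the findings as hypothesis-generating and prognostic, not predictive.

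Pooling cohorts 1 to 3, stratified by cohort, is optional. It would give 93 patients and 93 × 0.30 = 28 to 93 × 0.50 = 47 CBR events, but it assumes common effects across lung, gastrointestinal and pancreatic tumours and replaces the per-cohort question that the SAP emphasises.

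The cost is SAP wording and fewer tables, with no new data. The downside is that factors not listed in advance get only a univariate estimate.

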3.7.3 Planned Method of Analysis

Summary tables (descriptive statistics and frequency tables) will be provided for all baseline variables, efficacy variables, and safety variables, as appropriate. Continuous variables will be summarized with descriptive statistics (mean, standard deviation, range, and median). Ninety-five (95) percent confidence intervals (95% CI) may also be presented, as appropriate. Frequency counts and percentage of subjects within each category will be provided for categorical data.

The primary efficacy analysis will be performed using the binomial test procedure. Missing data will be treated using statistical multiple random imputation.

Concordance between investigator assessment and independent central radiology review will be analyzed using Cohen's Kappa. Although no significant differences are expected, a sensitivity analysis for the primary efficacy analysis will be performed using as response variable independent central radiology assessment.

Secondary endpoints will be summarized with descriptive statistics. Continuous variables will be summarized with n, mean, standard deviation, and range, frequency counts and percentage of subjects within each category will be provided for categorical data. Multivariate regression models will be used to study relations between explanatory variables and primary endpoint. Survival analysis will be performed to analyze PFS, Kaplan-Meier curves will be presented and possible comparisons will be tested using the log-rank test or the Cox proportional hazard model for multivariate analysis, hazard ratios (HR) and their 95% confidence interval (CI95%) will be provided. Patients with lost of follow-up or treatment discontinuation will be included in the final analysis of primary endpoint if they have at least one tumor evaluation and considered as censored data for survival endpoints.

R software version 3.2.1 will be used for all analysis.

Safety Analyses

Safety analyses will be based on the Safety Analysis Set. All safety analyses will be summarized separately by cohort. Adverse events and serious adverse events, laboratory test results, physical examination findings and vital signs, and their changes from baseline will be summarized using descriptive statistics. Abnormal values will be flagged.

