2.1 PRIMARY EFFICACY ANALYSES

The analysis of clinical benefit rate and overall survival rate will be performed independently for each study cohort when the last patient included in the corresponding cohort of the study will arrived to 9 months after inclusion in the study or have progressed. According to the protocol, the primary objective of the study will be based on the investigator assessment. 9-months clinical benefit rate (CBR) by Response Evaluation Criteria In Solid Tumors (RECIST version 1.1), which is defined as the percentage of patients achieving complete response (CR), partial response (PR), or stable disease (SD) at month 9 after durvalumab plus tremelimumab was started.

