2.1.1 Primary efficacy analyses in the Full Analysis Set

The primary endpoint for cohort 1, 2 and 3 is the CBR, nevertheless the result for all the cohorts will be shown below:

Table 92 Clinical benefit rate (investigator assessment) at 9 months in the Full Analysis Set

	Cohort 1	Cohort 2	Cohort 3	Cohort 4	Total
CBR at 9 months	n (% , CI 95%)				
Yes (CR, PR, SD)					
No (PD)					
Total	n (100%)				

The primary endpoint for cohort 4 is 9-months overall survival rate, which is defined as the percentage of patients alive at 9 months after durvalumab plus tremelimumab was started, nevertheless the result for all the cohorts will be shown in the following table.

Table 93 Overall survival rate at 9 months in the Full Analysis Set

	Cohort 1	Cohort 2	Cohort 3	Cohort 4	Total
Overall survival rate at 9 months	n (%), CI 95%				
Alive					
Death					
Total	n (100%)				

Concordance between investigator assessment and independent central radiology review will be analyzed using Cohen's Kappa. Although no significant differences are expected, a sensitivity analysis for the primary efficacy analysis will be performed using as response variable independent central radiology assessment.

Table 94 Agreement in CBR by Cohen's kappa coefficient in the Full Analysis Set

	Cohort 1	Cohort 2	Cohort 3	Cohort 4	Total
CBR at 9 months	Kappa k				
Investigator assessment vs. Independent review					

9-months clinical benefit rate (CBR) by Response Evaluation Criteria In Solid Tumors (RECIST version 1.1), according to independent central radiology.

Table 95 Clinical benefit rate (independent central radiology) at 9 months in the Full Analysis Set

	Cohort 1	Cohort 2	Cohort 3	Cohort 4	Total
CBR at 9 months	n (%), CI 95%				
Yes (CR, PR, SD)					
No (PD)					
Total	n (100%)				

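### Cohort 4's logistic model is fitted to month-9 clinical benefit, not to that cohort's primary endpoint, and at the planned rates no more than about 4 to 8 of 33 patients are expected to have that outcome

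*SAP*

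**What the plan says.** The general rule is in SAP section 3.7.3, with the same sentence in protocol section 11.2: "Multivariate regression models will be used to study relations between explanatory variables and primary endpoint". SAP section 2.1.1 fixes the endpoint: "The primary endpoint for cohort 4 is 9-months overall survival rate".

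SAP section 4.1 sets out the logistic models. They are fitted in each cohort "in order to determine predictor factors for response (CBR at 9 months"). Factors are screened one at a time, then removed by backward elimination until every remaining P value is below 0.05. No test is named for those P values. The cohort 4 shells are Tables 124 and 125 (body numbering; the list of tables at the front of the SAP gives them as 99 and 100). The first is titled "Univariate Logistic Regression for Response (CBR at 9 months) in cohort 4 (Full Analysis Set").

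Clinical benefit is defined in SAP section 2.1 as complete response, partial response or "stable disease (SD) at month 9 after durvalumab plus tremelimumab was started".

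For cohort 4, SAP section 3.6 states that "it is estimated that the reference proportion of patients being alive at 9 months is 13% and we expect an increase of 10" per cent, with 33 patients planned. SAP section 4.2.2 and Tables 140 and 141 plan Cox models of overall survival time in cohort 4. No model has survival status at 9 months as its outcome.

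**The concern.** The logistic template suits cohorts 1 to 3, where clinical benefit at 9 months is the primary endpoint. It is applied unchanged to cohort 4, whose primary endpoint is different. Read literally, section 4.1 leaves section 3.7.3 unfulfilled for that cohort: the SAP never says which model is its primary-endpoint model.

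The substitution also lands on a sparse outcome. Cohort 4 was planned around low survival at month 9, and patients with clinical benefit then are at most the survivors. Ordinary maximum-likelihood logistic regression with significance-based selection behaves badly when one outcome class has only a handful of patients. If a factor level contains no patient with the outcome, the odds ratio estimate is zero or infinite, and whether the factor is kept can depend on the test used. The report could then list predictors for cohort 4 that reflect the fitting method more than the patients. The primary test in cohort 4 is not affected.

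**Working it through.** **Inputs** (SAP section 3.6): 33 patients planned in cohort 4; 13% alive at 9 months (reference); 13% + 10% = 23% alive (expected).

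**The plan's own figure.** The final number follows from the stated one before loss: 30 × 1.10 = 33. The 30 does not follow from the stated inputs. The usual one-sample formula gives (1.645 + 0.842)² × 0.13 × 0.87 / (0.10 − 0.05)² ≈ 280. That is a separate matter; only the planned 33 and the two rates are used below.

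**Expected number alive at month 9.**
- At 13%: 33 × 0.13 = 4.29. Exact binomial 95% range 1 to 8; probability of more than 8 alive, 2%.
- At 23%: 33 × 0.23 = 7.59. Exact binomial 95% range 3 to 13; probability of more than 8 alive, 34%.

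Clinical benefit at month 9 requires being alive, so its expected count is no more than about 4 to 8. Every survivor who has progressed lowers it.

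**Risk of an empty cell.** Let k patients have the outcome, and let a binary factor unrelated to it split the 33 patients into a and 33 − a. The probability that all k fall on one side is [C(a,k) + C(33 − a,k)] / C(33,k).

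| k | 50/50 factor (16 and 17) | 30/70 factor (10 and 23) |
|---|---|---|
| 4 | (1,820 + 2,380) / 40,920 = 10% | (210 + 8,855) / 40,920 = 22% |
| 6 | (8,008 + 12,376) / 1,107,568 = 1.8% | (210 + 100,947) / 1,107,568 = 9% |
| 8 | (12,870 + 24,310) / 13,884,156 = 0.3% | (45 + 490,314) / 13,884,156 = 3.5% |

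These are risks per factor, and several factors would be screened.

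**What an empty cell does to selection.** Suppose all 4 patients with the outcome fall in the group of 16, and none in the group of 17. On the same data the Wald P value is 0.999 and the likelihood-ratio P value is 0.012. With 3 such patients the values are 0.998 and 0.031. Under a 0.05 rule the factor is dropped by one test and kept by the other, and section 4.1 does not choose between them.

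**Would changing the outcome alone cure this?** No. A logistic model of survival at 9 months still has about 4.3 to 7.6 patients in its smaller class. On a common convention of 5 to 10 outcomes per factor (an assumption, not in the documents), that supports 0.4 to 0.8 factors at 10 and 0.9 to 1.5 at 5. The Cox model of overall survival uses the deaths instead: 33 × 0.77 = 25.4 to 33 × 0.87 = 28.7 by month 9, with later deaths adding to that.

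**The case against.** Four objections deserve weight.

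- **The model serves a stated aim.** Section 4 is exploratory, and predictors of response are among its aims, with no exclusion of cohort 4. Section 2.1.1 also reports clinical benefit for all cohorts on purpose. Section 3.7.3 does not say that only the primary endpoint may be modelled. This stands. A reader might infer that Tables 124 and 125 answer a question the plan never asked, but the documents do not support that. What is missing is an identified primary-endpoint model for cohort 4.
- **Survival in cohort 4 is already modelled.** The Cox models in Tables 140 and 141 cover it, so survival predictors are not ignored. This stands too, and it makes the remedy small. Those models concern survival time, however, and the SAP does not link them to the 9-month endpoint.
- **The counts are expectations.** A reader might take 4 to 8 as a hard maximum. It is not one: at the expected 23%, more than 8 survivors would occur about one time in three. Nor do the documents support a figure of 2 to 4, which would need an assumed share of survivors already progressed; neither document gives one. With 6 to 8 patients the empty-cell risk for an evenly split factor is below 2%, so severe trouble is confined to the low end.
- **Screening with backward elimination is used in all cohorts.** True, and the general weakness of that method is not special to cohort 4. The planned rates make it sharper there: cohorts 1 to 3 plan on 31 × 0.30 = 9.3 to 31 × 0.50 = 15.5 patients with the outcome.

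A reader might also infer that Ki-67 would be useless as a factor in cohort 4 because eligibility puts nearly everyone in one band. The documents do not support this. The bands appear in a descriptive baseline table, the model shells name no factors, and eligibility can be met on mitotic count instead.

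**Conclusion.** The concern holds in limited form. For cohort 4, section 4.1 does not deliver what section 3.7.3 and protocol section 11.2 describe. The logistic model it does specify has an outcome expected in no more than about 4 to 8 of 33 patients. At 4, one evenly split factor in ten and more than one 30/70 factor in five would have an empty cell by chance alone; at 8 the figures are 0.3% and 3.5%. The risk of meaningless odds ratios and test-dependent selection is therefore material at the low end and small at the high end.

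This rests on full enrolment of 33, on true survival lying between the two planning rates, and on factors unrelated to outcome. It also assumes that deaths before month 9 count as no clinical benefit. The table shells label that category only as progression, so this is a reading of the definition, not an explicit statement. The point affects an exploratory result, not the primary test, but the correction is cheap and would change what is reported.

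**What to change.** In SAP section 4.1, state that the primary-endpoint modelling for cohort 4 is the Cox model of overall survival in Tables 140 and 141, and limit the claim that logistic models address the primary endpoint to cohorts 1 to 3.

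If a 9-month odds ratio is wanted in cohort 4, model alive at 9 months by Firth-penalised logistic regression. Use one or two factors named in advance and no stepwise selection, because the smaller class is still only about 4 to 8 patients.

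If the clinical benefit model is kept in cohort 4 for the response aim, fit it in the same way and label Tables 124 and 125 as exploratory and not the primary-endpoint model.

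The cost is a few sentences and two table shells. No new data are needed. What is given up is a stepwise search for predictors of clinical benefit in cohort 4, which the expected counts would not support.
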